8.7.1 Onset Date of Adverse Events

The onset date is the date that the event or the signs or symptoms related to the event started.

8.7.2 Resolution Date of Adverse Events

The resolution date is the date that the events or the signs/symptoms related to the event resolved or resolved with sequelae or enter the resolution date as the date when the patient has reached a new baseline if event is not expected to resolve.

8.7.3 Intensity of Adverse Events

The severity of each AE will be graded using the NCI CTCAE, Version 4.03 or later grading scale (https://ctep.cancer.gov/protocolDevelopment/electronic_applications/ctc.htm).⁴³

Severity is not the same as Serious.

For AEs not covered by NCI CTCAE, the severity will be characterized as mild, moderate, severe, life-threatening, or fatal according to the following definitions:

- Mild events are usually transient and do not interfere with the patient's daily activities
- Moderate events introduce a low level of inconvenience or concern to the patient and may interfere with daily activities
- Severe events interrupt the patient's usual daily activities and hospitalization (or prolongation of hospitalization) may be required
- Life-threatening events require urgent intervention to prevent death
- Fatal events are those events that led to the patient's death

8.7.4 Causal Relationship of Adverse Events to Rucaparib

Medical judgment should be used to determine the cause of the AE considering all relevant factors such as, but not limited to, the underlying study indication, coexisting disease, concomitant medication, relevant history, pattern of the AE, temporal relationship to the study medication, and de-challenge or re-challenge with rucaparib.

Table 6. Causal Relationship of Adverse Events to Rucaparib

Causality	Description
Not Related to Rucaparib	
• An AE that is clearly due to extraneous causes (eg, concurrent disease, concomitant medications, disease under study, etc.)• It does not follow a reasonable temporal sequence from administration of rucaparib• It does not follow a known pattern of response to rucaparib• It does not reappear or worsen when rucaparib is restarted• An alternative explanation is likely, but not clearly identifiable

Table 6. Causal Relationship of Adverse Events to Rucaparib

Causality	Description
Related to Rucaparib	
• An AE that is difficult to assign to alternative causes• It follows a strong or reasonable temporal sequence from administration of rucaparib• It could not be reasonably explained by the patient's clinical state, concurrent disease, or other concomitant therapy administered to the patient• It follows a known response pattern to rucaparib• It is confirmed with a positive re-challenge or supporting laboratory data

8.7.5 Outcome and Action Taken

The investigator will record the action taken and outcome for each AE according to the following criteria:

Action Taken with Study Drug (note all that apply)

- None
- Dose reduced/delayed
- Study drug temporarily interrupted
- Study drug permanently discontinued
- Other (specify)

Outcome

- Recovered
- Recovered with sequelae
- Recovering/ Resolving/ Improving
- Ongoing
- Death
- Lost to follow-up

8.8 Follow-up of Adverse Events, Serious Adverse Events, and Adverse Events of Special Interest

All AEs (including SAEs and AESIs) occurring during the study are to be followed up in accordance with good medical practice until resolved; judged no longer clinically significant; or, if a chronic condition, until fully characterized through 28 days after the last dose of rucaparib. Any SAEs, AESIs, and treatment-related Grade 3/4 AEs must be followed until

resolution or stabilization, death, or until lost to follow-up. After the 28-day window, treatment-related SAEs and all AESIs, irrespective of causality, need to be reported.

8.9 Regulatory Aspects of Serious Adverse Event and Adverse Events of Special Interest Reporting

All SAEs and AESIs, regardless of relationship to rucaparib, must be reported to the sponsor/SAE designee **within 24 hours** of knowledge of the event, during the study through 28 days after receiving the last dose of study treatment, according to the procedures below. After the 28-day specified window, only SAEs considered to be treatment-related and all AESIs, regardless of treatment relationship, should be reported. It is important that the investigator provide an assessment of relationship of the SAE or AESI to study treatment at the time of the initial report. The Serious Adverse Event (SAE)/ Adverse Events of Special Interest (AESI) Report Form must be used for reporting SAEs and AESIs. The contact information for reporting of SAEs and AESIs can be found on the SAE/ AESI Reporting Form and Pregnancy Report Forms.

The sponsor or its designee is responsible for submitting reports of AEs associated with the use of the drug that are both serious and unexpected to the US FDA, according to 21 Code of Federal Regulations (CFR) 312.32; to the European regulatory authorities according to the European Commission Clinical Trials Directive (2001/20/EC); and to other applicable regulatory authorities, according to national law and/or local regulations. All investigators participating in ongoing clinical studies with the study medication will receive copies of these reports for prompt submission to their IRB or IEC. In accordance with the European Commission Clinical Trials Directive (2001/20/EC), the sponsor or its designee will notify the relevant ethics committees in concerned member states of applicable suspected unexpected serious adverse reactions (SUSARs) as individual notifications or through periodic line listings.

The sponsor or its designee will submit all safety updates and periodic reports to the regulatory authorities as required by applicable regulatory requirements.

9 PLANNED STATISTICAL METHODS

9.1 General Considerations

Quantitative variables will typically be summarized using frequencies and percentages for appropriate categorizations and may also be summarized using descriptive statistics. For variables summarized with descriptive statistics, the following will be presented: N, mean, standard deviation (StD), median, minimum, and maximum. Categorical variables will be presented using frequencies and percentages.

The Kaplan-Meier methodology will be used to summarize time-to-event variables. If estimable, the 25th, 50th (median), and 75th percentiles with the 95% confidence interval (CI) will be summarized. The number of patients with events and the number of censored patients will also be presented.

All data will be used to their maximum possible extent, but without any imputations for missing data. Unless otherwise specified, baseline is defined as the last measurement on or prior to the first day of rucaparib administration.

All statistical analyses will be conducted with the SAS[®] System, Version 9.3 or higher. Further details regarding the statistical analyses planned in this study will be outlined in the SAP.

9.2 Analysis Populations

The following analysis populations are defined for the study:

Safety Population – The safety population will include all patients who received at least 1 dose of rucaparib.

Intent-to-treat Population (ITT) – The ITT population will include all patients who received at least 1 dose of rucaparib.

HRD-positive Population – Tumor tissue will be analyzed to determine the percentage of genomic LOH,³¹ and patients will be classified as HRD-positive or HRD-negative based on a prespecified LOH cut-off defined in the SAP. The HRD-positive population will include all patients who received at least 1 dose of rucaparib and are classified as HRD-positive.

9.3 Patient Disposition

Patient disposition will be summarized using frequency counts and the corresponding percentages. The number of patients in each analysis population, number of patients discontinued, and the primary reason for discontinuation will be summarized.

9.4 Demographics and Baseline Characteristics

Demographic (eg, age, race, and ethnicity as allowed by local regulations) and key baseline characteristics will be summarized for the safety and ITT populations.

9.5 Efficacy Analyses

All efficacy analyses will be conducted using the ITT and HRD-positive populations.

9.5.1 Primary Efficacy Analyses

The primary efficacy endpoint of ORR is defined as a best confirmed response of CR or PR by RECIST v1.1 ([Appendix 1](#)) as assessed by the investigator. The ORR will be summarized with frequencies and percentages for the ITT and HRD-positive populations as well as other HRD subgroups.

9.5.2 Secondary Efficacy Analyses

9.5.2.1 Duration of Response

Duration of confirmed response is defined as the time from the date that a response is first reported to the time that progression is first documented after the confirmed response.

9.5.2.2 Progression-free Survival

Progression-free survival (PFS) will be calculated as 1+ the number of days from the first dose of rucaparib to disease progression or death due to any cause, whichever occurs first. Patients without a documented event of progression will be censored on the date of their last adequate tumor assessment (ie, radiologic assessment) or date of first dose of rucaparib if no post-baseline tumor assessments have been performed.

9.5.2.3 Overall Survival

Overall survival (OS) is defined as the date from first dose of rucaparib to the date of death due to any cause. Patients who have not died will be censored at the date last known to be alive.

9.5.3 Exploratory Efficacy Analyses

9.5.3.1 Evaluation of Biomarkers of Response to Rucaparib

Next-generation sequencing (NGS) will be performed to measure defects in HRR genes and determine their correlation with response. Genomic alterations that may be assessed include deleterious mono- and bi- allelic variants in genes of the HRR pathway, genome-wide LOH, telomeric allelic imbalance (TAI), large-scale state transitions (LST), and tumor mutational burden. Patients will be classified based on the presence or absence of these markers of HRD, and possible associations of these biomarkers with response to rucaparib will be explored.

9.5.3.2 Evaluation of Circulating Tumor DNA as a Molecular Marker of Response

Pairwise comparisons will be performed for HRR genotyping results between centrally-assessed screening biopsy tissue, archival primary tissue (where available), and plasma ctDNA in all combinations. In particular, the concordance of genotyping results between

archival primary tissue and screening biopsy tissue will be assessed to explore whether the HRD status of the archival primary specimen accurately reflects that found in a screening tissue biopsy. Additionally, the sensitivity and specificity of plasma HRD assessment relative to the tissue results will be explored.

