While BRCA1/2 mutations are less prevalent in bladder cancer, targeted NGS of bladder cancer tumors has shown that approximately 11% of tumors have HRD resulting from mutations in DNA repair pathway genes.¹⁰ HRD has been demonstrated to predict response to cisplatin-based chemotherapy: patients with tumors that demonstrated evidence of HRD have been shown to benefit more from platinum chemotherapy than patients with tumors without evidence of HRD.^{10,11} In addition to deleterious mono- or bi- allelic alterations in HRR genes, tumors often have other genomic and/or epigenetic deficits that can drive HRD and cause distinct genomic signatures. For example, genome-wide LOH, telomeric allelic imbalance (TAI), and chromosomal breaks are all phenotypic markers of HRD that are prevalent in bladder cancer tumors. Analysis of The Cancer Genome Atlas (TCGA) bladder cancer data set (<http://cancergenome.nih.gov>) indicates that approximately 10% of bladder cancer tumors harbor a deleterious alteration in an HRR gene (Clovis, data on file). Additionally, genomic scars were detected in tumor samples without any HRR gene alterations, suggesting that, overall, approximately 60% of bladder cancer tumors may have HRD without having an alteration in a gene of the HRR pathway (Clovis, data on file). In the same data set, platinum-chemotherapy treated patients with above-median levels of HRD had improved survival when compared to patients with below-median levels of HRD: for these HRD subgroups the OS hazard ratio was 0.45 and statistically significant (Wald- $p=0.03$)(Clovis, data on file).

Given the prevalence of alterations in genes of the HRR pathway and the high incidence of non-mutation mediated HRD, it is reasonable to estimate that approximately 60% of all bladder cancer patients may exhibit HRD.

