3.2 Definition of HRD Signature

The HRD signature for this study is defined as the percentage of genome with loss of heterozygosity (LOH).³ Patients whose tumors have genome-wide LOH $\geq 10\%$ will be considered HRD-positive.

A mandatory tumor specimen is required for all patients; these tissue samples will be analyzed by Foundation Medicine, Inc. (FMI) using a next-generation sequencing (NGS) assay. This assay interrogates approximately 3,500 single-nucleotide polymorphisms (SNPs) across the genome and detects alterations in 310 genes.⁴ The SNPs on this panel will be used

to quantify the percentage of the genome with LOH, a marker of HRD shown to be associated with PARP inhibitor sensitivity in patients with relapsed ovarian cancer. This study will assess if LOH is correlated with PARP inhibitor sensitivity in patients with recurrent bladder cancer.

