9.3.1 Correlation of Biomarkers with Response to Rucaparib

In addition to the pre-specified cutpoint of 10% genome-wide LOH defining the HRD-positive population, the clinical activity of rucaparib will be evaluated in HRD-positive and HRD-negative groups defined by cutpoints across the range of all observed percent LOH values. Tumors will be analyzed by NGS to quantify the percentage of the genome with LOH and classified as HRD-positive and HRD-negative groups according to the LOH cutpoint. Outcome benefit in both groups will be evaluated.

Tumors with a deleterious alteration in a gene involved in homologous recombination repair (HRR), such as *BRCA1* and *BRCA2*, have been associated with rucaparib activity. The clinical activity of rucaparib in patients with a deleterious monoallelic or biallelic alteration in *BRCA1*, *BRCA2*, *PALB2*, *RAD51C*, and/or *RAD51D*, as well as other genes involved in homologous recombination DNA repair, will be evaluated. The activity of rucaparib in other biomarker-defined subgroups (e.g., microsatellite instability, tumor mutational burden, PD-L1 expression, gene expression profiling) may also be assessed.

9.3.2 Evaluation of Circulating Cell-free Tumor DNA as a Molecular Marker of Response to Rucaparib

Deleterious alterations in genes of the HRR pathway will also be interrogated using ctDNA extracted from baseline plasma samples. The clinical activity of rucaparib will be evaluated in subgroups of patients with a HRR gene alteration, as well as in subgroups of patients with other alterations detected in the ctDNA assay.

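### Protocol 9.5.3.2 asks whether archival tissue reproduces HRD status but compares HRR genotypes; the trial defines HRD by genomic LOH, so this exploratory analysis cannot answer its own question

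*Protocol*

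**What the plan says.** Protocol 9.5.3.2 sets out the comparison: "Pairwise comparisons will be performed for HRR genotyping results between centrally-assessed screening biopsy tissue, archival primary tissue", with plasma ctDNA as the third source and archival tissue used only where it exists. It gives the purpose of the tissue comparison in terms of HRD: "archival primary tissue and screening biopsy tissue will be assessed to explore whether the HRD status of the archival primary specimen accurately reflects that found" (reference: screening biopsy). For plasma it adds that "the sensitivity and specificity of plasma HRD assessment relative to the tissue results will be explored". It names no concordance statistic and does not say what plasma HRD assessment measures.

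HRD status is defined elsewhere. Protocol 3.1 and 9.2 classify patients by percentage of genomic LOH against a cut-off to be given in the SAP. SAP 3.2 states: "The HRD signature for this study is defined as the percentage of genome with loss of heterozygosity (LOH"), and sets the cut-off at 10% or more.

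Protocol 1.2 supplies the prevalences. The TCGA analysis "indicates that approximately 10% of bladder cancer tumors harbor a deleterious alteration in an HRR gene". A targeted sequencing study gives about 11% for HRD due to DNA-repair gene mutations. HRD overall is put at about 60%.

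On ctDNA, SAP 9.3.2 says: "Deleterious alterations in genes of the HRR pathway will also be interrogated using ctDNA extracted from baseline plasma samples". It also covers other ctDNA alterations but does not mention LOH. The SAP contains no archival-versus-screening concordance analysis.

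**The concern.** The analysis measures one variable and draws its conclusion about another. Protocol 1.2 itself explains why they differ: genomic signatures are valued because they pick up HRD whatever its cause, and most HRD in bladder cancer is expected to occur without an HRR-gene alteration. A patient with no HRR alteration in either specimen counts as concordant, whatever the percent LOH is in each.

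At stake is what may be said about specimen choice. The eligibility criteria accept existing tissue in place of a new biopsy only if it was collected within 6 months with no intervening treatment. Whether older archival tissue gives the same HRD call is therefore a practical question for later studies. A report that archival HRD status matches the biopsy, resting on genotype agreement, would not be supported by the data behind it.

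**Working it through.** **Inputs.** HRR-altered fraction p = 0.10 or 0.11 (Protocol 1.2). HRD-positive fraction 0.60 (Protocol 1.2 and 9.9). Enrollment 200 (Protocol 9.9). Assumptions: these prevalences apply to the trial and to the 10% LOH cut-off; prevalence is the same in both specimens; all 200 patients have pairs. The last is generous, since archival tissue is used only where available.

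**1. The plan's own figure.** 200 × 0.60 = 120 HRD-positive patients, as stated. The documents give no expected concordance.

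**2. How much of HRD the genotype can see.** Suppose every HRR-altered tumor is also LOH-positive, the most favorable case.
- Share of HRD-positive patients identified: 0.10/0.60 = 16.7%, or 0.11/0.60 = 18.3%.
- HRD-positive patients with no HRR alteration in screening tissue: 120 − 20 = 100, or 120 − 22 = 98.
- One sentence in Protocol 1.2 can be read as placing the whole 60% in tumors without an HRR alteration. The share is then lower: 0.10/0.70 = 14.3%, or 0.11/0.71 = 15.5%.

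**3. Agreement by chance.** For two unrelated calls with prevalence p, agreement = p² + (1 − p)².
- HRR genotype: 0.10² + 0.90² = 0.820; 0.11² + 0.89² = 0.804.
- LOH status: 0.60² + 0.40² = 0.520.

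**4. Genotype agreement when carriers are partly shared.** If a fraction s of altered tumors is altered in both specimens, agreement = 1 − 2p(1 − s) and kappa = (agreement − chance)/(1 − chance). At p = 0.10:

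| s | Raw agreement | Kappa |
|---|---|---|
| 0.50 | 0.90 | 0.44 |
| 0.75 | 0.95 | 0.72 |
| 0.90 | 0.98 | 0.89 |

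**5. Does kappa rescue the analysis?** A hypothetical case tests the logic; it is not a forecast. Take s = 0.90, all carriers LOH-positive, and LOH unrelated between specimens in non-carriers. Non-carriers are then LOH-positive with probability (0.60 − 0.10)/0.90 = 0.556.
- Both specimens altered (0.09): LOH always agrees, contributing 0.090.
- One altered (0.02): 0.02 × 0.556 = 0.011.
- Neither altered (0.89): 0.89 × (0.556² + 0.444²) = 0.89 × 0.506 = 0.450.

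LOH agreement is about 0.55, so LOH kappa = (0.55 − 0.52)/0.48, about 0.07, while genotype kappa is 0.89. Kappa corrects for chance, not for the choice of variable.

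**6. Plasma.** Sensitivity against tissue genotype is not inflated by low prevalence; it equals the detected fraction. It rests on about 20 altered tumors, so 15/20 has an exact 95% CI of 51-91%. If plasma reads HRR genes only and is scored against LOH status, its true-positive detections cannot exceed the 17-18% ceiling in step 2.

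**The case against.** Several counter-arguments carry weight.

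- The paragraph is exploratory and has no decision rule. SAP 9.3 allows exploratory analyses to be dropped. This stands and limits the importance of the point.
- Protocol 9.5.3.1 lists HRR variants beside LOH, TAI and LST as markers of HRD, so HRD status in 9.5.3.2 may just be loose wording. That is plausible, but only HRR genotyping is carried into the comparison, and Protocol 9.2 gives HRD status a specific meaning.
- Protocol 9.8.2 follows molecular profiles in matched archival, pre- and post-treatment tissue without restricting the alterations. It does not exclude LOH, but it concerns resistance. Neither it nor SAP 9.3.3 names LOH or an agreement analysis.

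A reader might also infer more than the documents support.

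- *That agreement will look near-perfect.* Raw agreement of 98% needs about 90% of altered tumors to be shared. No such figure is given, and no statistic is named.
- *That LOH is known to shift between a primary tumor and a later metastasis.* Protocol 1.2 says only that LOH results from accumulated DNA damage in HRD tumors. Whether status carries over is the open question.
- *That the plan would declare plasma able to detect HRD.* The plasma measure is undefined, and an HRR-only reading is an inference from the surrounding text and SAP 9.3.2. Scored against LOH, low sensitivity would be visible. Scored against tissue genotype, the analysis is sound and only its label is wrong.

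**Conclusion.** The mismatch is real. Genotype concordance cannot show whether LOH-defined HRD status carries over between specimens, whichever statistic is used. On the protocol's prevalences, HRR genotype captures at most about 17-18% of HRD-positive patients. Raw genotype agreement starts from a chance level of about 80-82%, against 52% for LOH status. These figures assume that the quoted prevalences hold in the trial, are equal in both specimens, and that the 60% applies at the 10% LOH cut-off.

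The reach is limited. It would be tempting to conclude that the HRD-positive population is compromised, but it is not: patients are classified by LOH on the mandatory pre-treatment specimen. Nothing in 9.5.3.2 feeds eligibility, the primary ORR or the interim rule. The point is worth correcting because the analysis as written cannot answer its stated question and the remedy is cheap.

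**What to change.** In Protocol 9.5.3.2, and as an added analysis in the SAP (for example in section 9.3):

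- For archival-screening tissue pairs with two evaluable LOH results, report positive agreement, negative agreement and kappa at the 10% LOH cut-off, each with a 95% CI. Add the paired difference in percent LOH.
- Keep HRR-genotype concordance as a separate analysis, with no statement about HRD status.
- Define plasma HRD assessment. Otherwise limit its sensitivity and specificity to detection of HRR-gene alterations against tissue HRR genotype.

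The cost is a text change and one extra exploratory table. No new patient procedure is needed: Protocol 7.6.5.2 already collects archival tissue for molecular profiling, and the SAP 3.2 panel yields percent LOH as well as gene alterations. This assumes archival samples are run on that panel, which the documents do not state. Only pairs with evaluable LOH in both specimens contribute, so intervals will be wider than with all genotyped pairs.

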9.6 Pharmacokinetic Analyses

In all patients with at least 1 PK sample collected, the trough plasma rucaparib PK data (C_{min}) and summary statistics (N, mean, StD, minimum, median, maximum, coefficient of variation [CV]%) will be reported.

